4 SELECTION AND WITHDRAWAL OF PATIENTS

4.1 Inclusion Criteria

Individuals should meet all the following criteria to be considered eligible to participate in the study:

- 1. Provision of full informed consent prior to any study-specific procedures.
- 2. Patients must be ≥ 18 years of age, at the time of signing informed consent.
- 3. Female patients who have histologically and/or cytologically confirmed locally advanced or metastatic breast cancer that has progressed following at least one line of therapy.
- 4. Patients with at least one measurable lesion per RECIST version 1.1 at baseline that can be accurately assessed by CT scan or MRI and is suitable for repeated assessment at follow up-visits.
- 5. ECOG performance status 0 to 2.
- 6. Life expectancy of at least 3 months.
- 7. Adequate bone marrow, liver and renal functions as assessed within 7 (± 2) days before the first dose of study drug with the following laboratory requirements:
 - a. Hemoglobin ≥ 8.0 g/dL (should not be transfused or treated with erythropoietin to maintain or exceed this level)
 - b. Absolute neutrophil count (ANC) $\geq 1.0 \times 10^9 / L$ without growth factor support

CONFIDENTIAL Page 27 of 66

- c. Platelet count $> 75 \times 10^9/L$
- d. Total bilirubin ≤ 1.5 times the ULN (or ≤ 3 x ULN, if the patient has Gilbert syndrome)
- e. ALT and AST \leq 3 x ULN (\leq 5 x ULN for patients with liver metastasis or liver involvement)
- f. Creatinine clearance ≥ 50 mL/min (calculated using the Cockcroft-Gault formula) for patients with creatinine levels above ULN.
- 8. Female patient of childbearing potential should be willing to use a medically acceptable method of contraception as defined in Appendix B while participating in the study and for 30 days after the last dose of study drug AND must have a negative serum pregnancy test within 3 days prior to Cycle 1 Day 1 (C1D1).
- 9. Ability to swallow and retain oral medication.
- 10. Willingness and capability to comply with the study requirements.

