7.6 Dose Modifications

In case of hematologic and non-hematologic toxicities, the dose modifications provided below (**Table 6** and **Table 7**) should be used as a guidance and should be determined as per PI's clinical judgement. The dose modifications are intended to be applied when the investigator determines the events related to tenalisib. If events (cytopenia) are deemed related to the underlying disease rather than tenalisib, dose reduction will be done as per the investigator's discretion. In case of drug withhold, tenalisib treatment can be resumed if:

- Patient recovers from grade 3-4 toxicity as defined in dose modification guidance below.
- No clinical or radiographic evidence of disease progression.
- Investigator believes the risk of progression outweighs the risk of further treatment.

If treatment is delayed >2 weeks, treatment continuation should be discussed with Medical monitor. The treatment should be permanently discontinued if withhold of study drug due to drug related toxicity is for > 28-days unless approved by medical monitor.

At the discretion of the investigator, a dose re-escalation may be permitted for patients who earlier has dose reduction. The decision should be taken after evaluating the emerging safety data and benefit and risk of re-escalation. Drug holidays are discouraged. Any patient in whom similar toxicity recurs at the reduced dose, it should be discussed with medical monitor to determine appropriate strategy on treatment continuation.

CONFIDENTIAL Page 46 of 66

Table 6: Dose modifications for hematologic toxicity

| CTCAE Grade | Action to be Taken |
|--|---|
| Hematologic toxicity | |
| Grade 3 Neutropenia $(1.0 \times 10^9/L < ANC \ge 0.5 \times 10^9/L)$ | Maintain dose level.Monitor ANC at least weekly. |

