| Grade 4 Neutropenia (0.5 x 10 ⁹ /L <anc)< th=""> First incidence: Hold dose until resolved to ≤ Grade 2 or baseline. Monitor ANC at least weekly. Resume treatment at the same dose level. Subsequent occurrence: Hold dose until resolved to ≤ Grade 2 or baseline, consider growth factor support. Resume treatment at one dose lower* if warranted. Discontinue if further dose modification required at lowest dose. 	</anc)<> | First incidence: Hold dose until resolved to ≤ Grade 2 or baseline. Monitor ANC at least weekly. Resume treatment at the same dose level. Subsequent occurrence: Hold dose until resolved to ≤ Grade 2 or baseline, consider growth factor support. Resume treatment at one dose lower* if warranted. Discontinue if further dose modification required at lowest dose. |
| Grade 3 Febrile neutropenia ANC <1.0 X 10^9 /L with a single temperature of > 38.3^0 C (101^0 F) or a sustained temperature of $\ge 38^0$ C (100.4^0 F) for more than one hour. | Withhold dose until resolved to ≤ Grade 2 or baseline, consider growth factor support, then reduce by 1 dose level*, if warranted. If the ANC is <1 X 10⁹/L (1000/μL) before therapy, the dose shall not be modified as long as ANC >0.5 X 10⁹/L. |
| Grade 3 Thrombocytopenia $(50.0 \times 10^9 / L < PLT \ge 25.0 \times 10^9 / L)$ with Grade 1 bleeding | Maintain dose level.Monitor platelet count at least weekly. |
| Grade 4 thrombocytopenia (20.0 X 10 ⁹ /L< PLT) OR Grade 3 thrombocytopenia with Grade 2 bleeding | 1st occurrence: Hold dose until to ≤ Grade 2 or baseline or resolution of bleeding. Consider platelet transfusion as necessary. Resume treatment at the same dose level. Subsequent Occurrences: Hold dose until to ≤ Grade 2 or baseline or resolution of bleeding. Consider platelet transfusion as necessary. Resume treatment at one dose lower* if warranted. Discontinue if further dose modification required at lowest dose*. |

Note: The drug interruption and dose modification should be discussed with medical monitor.

CONFIDENTIAL Page 47 of 66

^{*}See 'Guidelines for dose reduction' below.

Table 7: Dose modifications for non-hematologic toxicity

| | eations for non-hematologic toxicity |
|--------------------------|--|
| Non-Hematologic Toxicity | |
| Infection | Grade 3 or higher sepsis or pneumonia |
| | Withhold tenalisib until infection has resolved. |
| | • Restart at the same or at the reduced dose level*, if warranted. |
| Skin rash (Cutaneous | Grade 1-2 |

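### Four rows of Table 6 print the inequality before ANC or PLT the wrong way round, so the Grade 4 count limits cover every eligible patient and miss the lowest counts

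*Protocol*

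**What the plan says.** Table 6 in Protocol section 7.6 pairs each haematologic grade with a count range and an action. Counts here and below are x10^9/L.

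- Grade 3 neutropenia is given as "1.0 \times 10^9/L < ANC \ge 0.5 \times 10^9/L". Action: keep the dose and check ANC at least weekly.
- Grade 4 neutropenia begins "Grade 4 Neutropenia (0.5 x 10" and continues with a less-than sign followed by ANC, so the condition reads 0.5 < ANC. Action: hold.
- Grade 3 thrombocytopenia is given as "50.0 \times 10^9 / L < PLT \ge 25.0 \times 10^9 / L", together with Grade 1 bleeding. Action: keep the dose and check platelets at least weekly.
- Grade 4 thrombocytopenia sets 20 against the count as "L< PLT) OR Grade 3 thrombocytopenia with Grade 2 bleeding". Action: hold.

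The febrile neutropenia row of the same table uses the opposite direction. It starts at ANC below 1.0 and, for patients already below 1.0 before therapy, says "the dose shall not be modified as long as ANC >0.5 X" 10^9/L.

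On entry, inclusion criterion 7b (section 4.1) requires "Absolute neutrophil count (ANC) $\geq 1.0 \times 10^9 / L$ without growth factor support". Criterion 7c requires platelets above 75 in section 4.1, and at least 75 in the synopsis.

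Section 7.6 says of Tables 6 and 7 that they "should be used as a guidance and should be determined as per" the investigator's clinical judgement, for events considered related to tenalisib. The note under Table 6 adds: "The drug interruption and dose modification should be discussed with medical monitor".

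**The concern.** These limits decide between keeping and holding the dose. If the printed sign is followed, an ANC of 0.7 triggers a hold where the grade name calls for continuing, and an afebrile patient with an ANC of 0.3 meets no printed limit at all.

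The events are expected. Protocol section 1.4 reports related Grade 3 or higher neutropenia in 4.4% of patients and thrombocytopenia in two, and section 3.4.5 asks sites to monitor for neutropenia.

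Holds also have consequences. A repeat Grade 4 event can lead to a lower dose, Group 1 has only one reduction step before discontinuation (Table 8), and a drug-related hold of more than 28 days ends treatment unless the medical monitor approves otherwise. The trial is meant to choose between two doses partly on tolerability (section 1.5.2), so sites should apply the same thresholds.

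**Working it through.** **Inputs.** The four printed limits and the febrile neutropenia row come from Table 6. The entry limits come from section 4.1 and the synopsis.

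**Step 1: reduce the printed conditions.**

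- Grade 3 neutropenia: 1.0 < ANC and ANC ≥ 0.5 reduces to ANC > 1.0.
- Grade 4 neutropenia: 0.5 < ANC is ANC > 0.5.
- Grade 3 thrombocytopenia: 50 < PLT and PLT ≥ 25 reduces to PLT > 50.
- Grade 4 thrombocytopenia (count part): 20 < PLT is PLT > 20.

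In the two Grade 3 rows the lower bound (≥ 0.5, ≥ 25) is right and only the upper-limit sign is wrong.

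**Step 2: turn the sign.** This gives 0.5 ≤ ANC < 1.0, ANC < 0.5, 25 ≤ PLT < 50 and PLT < 20.

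**Step 3: compare at example counts (T = limit met, F = not met).**

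| ANC | 0.3 | 0.5 | 0.7 | 1.0 | 1.5 | 4.0 |
|---|---|---|---|---|---|---|
| Grade 3 as printed | F | F | F | F | T | T |
| Grade 3 corrected | F | T | T | F | F | F |
| Grade 4 as printed | F | F | T | T | T | T |
| Grade 4 corrected | T | F | F | F | F | F |

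| Platelets | 10 | 20 | 22 | 30 | 60 | 200 |
|---|---|---|---|---|---|---|
| Grade 3 count as printed | F | F | F | F | T | T |
| Grade 3 count corrected | F | F | F | T | F | F |
| Grade 4 count as printed | F | F | T | T | T | T |
| Grade 4 count corrected, limit 20 | T | F | F | F | F | F |
| Grade 4 count corrected, limit 25 | T | T | T | F | F | F |

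The platelet table concerns counts only. The Grade 3 row also needs Grade 1 bleeding, and the Grade 4 row can also be reached through Grade 3 thrombocytopenia with Grade 2 bleeding. A febrile patient with an ANC of 0.3 is still held under the febrile neutropenia row.

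**Step 4: apply the entry limits.** Any ANC of at least 1.0 exceeds 0.5, and any platelet count of 75 or more exceeds 20. All eligible patients therefore meet both printed Grade 4 count limits. After correction none does.

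**Step 5: look for what remains.** With the sign turned and 20 kept, counts from 20 to below 25 fail both PLT ≥ 25 and PLT < 20, so they meet neither count limit. A Grade 4 limit of 25 removes the gap.

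**Step 6: consider a display fault.** The same direction appears in all four rows, while the febrile neutropenia row carries its signs correctly. That pattern points to the table itself.

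**The case against.** The strongest reply is that no clinician would read the table this way. The first column is headed by CTCAE grade, each row opens with a grade name, and the protocol grades adverse events by CTCAE version 5.0. The bracketed range only explains that name. The literal reading also defeats itself: the Grade 4 action is to hold until the count is back to Grade 2 or baseline, so a patient at baseline would be held until she reached the state she is already in. The table is guidance, the medical monitor is involved, and nothing in the documents shows a dose wrongly held or continued.

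Most of this stands as a limit on harm. The row headed Grade 4 neutropenia does exist and does order a hold; it is the printed range that leaves out the lowest counts. None of this makes the range right, and an operative threshold should not depend on the reader spotting that it is reversed.

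Two narrower points also stand. The febrile row's clause about ANC above 0.5 concerns patients whom criterion 7b would normally exclude, so that row's opening limit of ANC below 1.0 is the better evidence of intended direction. And because investigators may depart from the table, a hold that differs from it is not in itself an error, so a look back at recorded holds can only be descriptive.

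**Conclusion.** The concern holds. Four count limits in Table 6 are wrong as written, and the table contradicts its own grade names and its febrile neutropenia row. As printed, both Grade 4 count limits include all eligible patients and exclude ANC of 0.5 or less and platelets of 20 or less.

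The conclusion rests on reading the inequalities literally and on the signs being as printed. It needs no outside grading source to establish direction. The choice between 20 and 25 for the Grade 4 platelet limit is a separate medical decision.

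The risk is inconsistent dose holds between sites, reduced by the safeguards above. No analysis error is claimed: the SAP does not derive grades from Table 6, and the footnote to its Table 14.1.1.1 takes dose reductions from the treatment exposure page of the eCRF. This should be corrected, but it does not threaten the trial's results.

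**What to change.** Reprint the four limits (x10^9/L):

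- Grade 3 neutropenia: 0.5 ≤ ANC < 1.0
- Grade 4 neutropenia: ANC < 0.5
- Grade 3 thrombocytopenia: 25 ≤ PLT < 50, with Grade 1 bleeding as now
- Grade 4 thrombocytopenia: PLT below the limit confirmed by the sponsor's medical or safety team; 25 leaves no gap to Grade 3

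SAP section 5.1 says the study was closed early, so the route depends on who is still treated. If any patient remains on tenalisib, send sites a one-table correction by administrative letter or amendment. If none does, file an erratum and compare recorded haematologic holds with the ANC and platelet counts already recorded for about 40 patients, reporting the result descriptively. Neither route needs new data.

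### Table 6 lets a patient held for a Grade 4 platelet count restart at Grade 4 once bleeding has stopped

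*Protocol*

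**What the plan says.** Protocol section 7.6, Table 6, has one row for two situations: a Grade 4 platelet count, and, as its second trigger, "OR Grade 3 thrombocytopenia with Grade 2 bleeding". Both share one release rule: "Hold dose until to ≤ Grade 2 or baseline or resolution of bleeding". After a first occurrence the row continues: "Consider platelet transfusion as necessary. Resume treatment at the same dose level". The same rule is printed again for later episodes, "Subsequent Occurrences: Hold dose until to ≤ Grade 2 or baseline or resolution of bleeding", followed by a restart one dose level lower if warranted.

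Other text bearing on the restart:

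- Section 7.6 lists general conditions for resuming drug. The one on recovery reads "Patient recovers from grade 3-4 toxicity as defined in dose modification guidance below". The others are no evidence of progression and an investigator judgement of risk.
- The tables are described as guidance under the investigator's clinical judgement. A note under Table 6 adds: "The drug interruption and dose modification should be discussed with medical monitor".
- The Grade 4 neutropenia row of the same table releases on the count alone: "First incidence: Hold dose until resolved to ≤ Grade 2 or baseline".
- The milder platelet row (Grade 3 with Grade 1 bleeding) keeps the dose and asks for "Monitor platelet count at least weekly". The more severe row has no such instruction.

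**The concern.** Two of the three release alternatives are platelet levels. The third, resolution of bleeding, is a symptom and sets no level. Because the alternatives are joined by 'or' and apply to both triggers, a patient held for a Grade 4 count meets a release condition as soon as a bleed stops, whatever the count then is.

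The rule decides when drug is given again after a potentially serious toxicity. Followed literally at a first occurrence, it permits the full assigned dose at a Grade 4 count shortly after a bleed: 2 × 800 = 1600 mg/day in Group 1 or 2 × 1200 = 2400 mg/day in Group 2.

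The stake is patient safety only. Both groups use the same table and the safety analysis is descriptive, so no bias between doses and no effect on an efficacy endpoint is alleged.

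**Working it through.** **1. Apply the rule case by case.** Take a patient held for a Grade 4 count who has bled, and list every later state. Compare the rule as printed with two stricter rules.

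| Platelet grade now | Bleeding | As printed (any alternative) | Count only | Count and bleeding |
|---|---|---|---|---|
| 4 | ongoing | hold | hold | hold |
| 4 | resolved | **release** | hold | hold |
| 3 | ongoing | hold | hold | hold |
| 3 | resolved | **release** | hold | hold |
| 2 or 1 | ongoing | release | release | hold |
| 2 or 1 | resolved | release | release | release |

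The point concerns the Grade 4, bleeding-resolved line.

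**2. Identify which alternative opens the route.** Grade 2 or lower means at least 50 × 10⁹/L, by the upper figure that Table 6 prints for Grade 3. The baseline alternative cannot release at Grade 4 either, because inclusion criterion 7c requires platelets of about 75 × 10⁹/L at entry. Only the bleeding alternative can.

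**3. Look for another barrier.** The recovery condition in section 7.6 refers back to the table, so it inherits the same rule. The conditions on progression and investigator risk judgement, and the medical monitor note, name no platelet level. Extra counts are allowed when clinically indicated (section 6.1; Table 5, footnote 7), but this row does not require one. The two count alternatives cannot be judged without a count; the bleeding alternative can.

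**4. Compare with the protocol's own standard.** Grade 4 neutropenia is released only on the count. In Table 7, other Grade 4 non-hematologic toxicities restart only at Grade 2 or lower.

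**5. Bound the frequency.** Protocol section 1.4 mentions thrombocytopenia in two patients, among Grade ≥3 laboratory abnormalities. The text gives 169 exposed patients, but its printed percentages (15.6, 11.9, 7.4, 4.4) do not fit 169. The nearest values there are 15.4 or 16.0, 11.8 or 12.4, 7.1 or 7.7, and 4.1 or 4.7. Among all N from 30 to 199, only 135 reproduces all four: 21/135, 16/135, 10/135 and 6/135. Both denominators are therefore shown, with exact (Clopper-Pearson) 95% limits. Expected cases are 40p, and the chance of at least one is 1 − (1 − p)⁴⁰.

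| | p | Expected in 40 | At least one |
|---|---|---|---|
| 2/135 | 1.48% (0.18% to 5.25%) | 0.59 (0.07 to 2.10) | 0.45 (0.07 to 0.88) |
| 2/169 | 1.18% (0.14% to 4.21%) | 0.47 (0.06 to 1.68) | 0.38 (0.06 to 0.82) |

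These figures are for the reported thrombocytopenia, not for the narrower event at issue. They are upper figures.

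**The case against.** The strongest reply is that the harmful reading is not the natural one. Only the second trigger mentions bleeding, so resolution of bleeding belongs to it, and the count alternatives belong to the Grade 4 trigger. The row above supports this: a Grade 3 count with only Grade 1 bleeding needs no hold. The literal reading also undermines itself, since a patient restarted at Grade 4 still meets the row's condition for a hold, and a patient at Grade 4 has not recovered in any ordinary sense. This is probably what the authors intended. But the row does not pair the alternatives with the triggers, and the recovery condition takes its meaning from the table. That the row would both hold and release the same patient is a further reason to correct it.

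Second, the table is guidance, with investigator judgement and the medical monitor behind it. That lowers the practical risk, but neither safeguard supplies a threshold.

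Third, on monitoring: section 4.3 asks that drug-related Grade ≥3 laboratory abnormalities be followed until Grade 2 or lower, Table 5 schedules regular blood counts, and the febrile neutropenia row also lacks a weekly count. The omission is therefore not unique to this row. However, follow-up of a value is not a condition for restarting, and the omission matters more where one release alternative needs no count.

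Fourth, the frequencies describe a broader event in patients with hematological malignancies. That is correct, and they should be read only as a ceiling.

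**Conclusion.** The concern holds as a minor defect in a safety rule. As printed, Table 6 allows drug to restart at a Grade 4 platelet count once bleeding has resolved, and at a first occurrence the restart is at the same dose. The finding is confined to that route. It does not cover a Grade 4 patient who never bled, or one still bleeding after the count has recovered.

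At most about half a case would be expected in 40 patients (0.59 on a denominator of 135, 0.47 on 169), with wide limits. This assumes that the earlier rate carries over to breast cancer patients at these doses. The true figure for this route is lower, because Grade 4 with resolved bleeding is a subset, and the documents report no such case. Confidence in the reading of the text is high.

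**What to change.** Split the release rule by trigger, for first and subsequent occurrences alike:

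- **Grade 4 count:** hold until platelets are at Grade 2 or lower, or back to baseline.
- **Grade 3 count with Grade 2 bleeding:** hold until platelets are at Grade 2 or lower or back to baseline, or until bleeding has resolved. Requiring bleeding at Grade 1 or lower would match the row above.
- **Both:** carry down the instruction "Monitor platelet count at least weekly" for the duration of the hold.

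The existing 28-day limit on holds in section 7.6 needs no change.

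SAP section 5.1 records that the study closed early, so the new wording is for any later use of this table. For the present report, use planned Listings 16.2.5.1 (drug exposure), 16.2.7.1 (adverse events) and 16.2.8.1.1 (hematology) to check the platelet count at restart after any hold under this row.

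The cost is the wording of one table row and a weekly local platelet count while a patient is on hold. No patients or visits are added beyond that, and the check uses outputs already planned.

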7.4.3 Abnormal Laboratory Values

Any grade 3 or 4 laboratory abnormalities and clinically significant grade 1 or 2 laboratory value(s) should be recorded as an AE. Isolated laboratory abnormality without clinical significance should not be captured as AE if confirmed by the investigator. If an abnormal laboratory value or vital sign is associated with clinical signs and/or symptoms, the sign or symptom should be reported as an AE, and the associated laboratory value or vital sign should be considered additional information that must be collected on the relevant eCRF. If the laboratory abnormality is a sign of a disease or syndrome, only the diagnosis needs to be recorded on the SAE Report Form or AE eCRF.

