| reactions) | • Maintain tenalisib dose. Initiate supportive care with emollients, |
| | antihistamines (for pruritus), or topical steroids |
| | Monitor closely until resolved. |
| | Grade 3 |
| | • Withhold tenalisib dose. Initiate supportive care with emollients, |
| | antihistamines (for pruritus), or topical steroids |
| | Monitor at least weekly until resolved. |
| | • Restart tenalisib at the reduced dose level*. |
| | • If severe cutaneous reaction does not improve, worsens, or |
| | recurs, discontinue tenalisib. |
| | Life threatening or SJS, TEN, DRESS (any grade) |
| | Discontinue tenalisib permanently. |
| Pneumonitis without | Moderate (Grade 2) symptomatic pneumonitis |
| suspected infectious | • Withhold tenalisib dose. Initiate systemic steroid therapy. If |
| cause | pneumonitis recovers to Grade 0 or 1, tenalisib may be resumed |
| | at reduced dose*. |
| | • If non-infectious pneumonitis recurs or patient does not respond |
| | to steroid therapy, discontinue tenalisib. |
| | Severe (Grade 3) or life-threatening pneumonitis |
| | Discontinue tenalisib. Treat with systemic steroid therapy. |
| Non-infectious Diarrhea | Moderate diarrhea, responsive to antidiarrheal agents: |
| | Maintain tenalisib dose. Monitor at least weekly until resolved. |
| | Moderate diarrhea, unresponsive to antidiarrheal agents: |
| | • Withhold tenalisib dose. Initiate supportive therapy with enteric |
| | acting steroids (e.g., budesonide). |
| | Monitor at least weekly until resolved. |
| | • Restart tenalisib at the reduced dose level*. |
| | Severe diarrhea or hospitalization: |
| | • Withhold tenalisib dose. Initiate supportive therapy with enteric |
| | acting steroids (e.g., budesonide) or systemic steroids. |
| | Monitor at least weekly until resolved. |
| | • Restart tenalisib at the reduced dose level*. |
| | Life threatening diarrhea: |
| | Discontinue tenalisib permanently. |
| Hepatic* | Transaminitis |
| | Grade 1-2 Transaminitis (ALT/AST >1-3 x ULN if baseline is |
| | normal; 1.5 -3 x baseline if baseline is abnormal): |

CONFIDENTIAL Page 48 of 66

| | Maintain tenalisib dose and initiate prednisone 40 mg daily. | | | |
|--------------------------|--|--|--|--|
| | Monitor AST/ALT weekly until resolved and then taper steroid. | | | |
| | • Withhold tenalisib in case of development of grade 2 | | | |
| | transaminitis or worsening of Grade 1 transaminitis while on | | | |
| | steroids. | | | |

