| | Grade 3 Transaminitis (ALT/AST >5–20 x ULN; >5-20 x | | | |
| | baseline if baseline is abnormal): | | | |
| | Withhold tenalisib and monitor ALT/AST twice a weekly until | | | |
| | Grade ≤1; restart tenalisib at one dose lower*. | | | |
| | Initiate prednisone 1 mg/kg in case no improvement after | | | |
| | withholding tenalisib for 1 week. | | | |
| | • Monitor ALT/AST twice a weekly until Grade ≤1; restart | | | |
| | tenalisib at one dose lower* and taper steroid. | | | |
| | • If no immediate response to steroids within 7 days, initiate | | | |
| | mycophenolate mofetil. | | | |
| | • Discontinue if further dose modification required at lowest dose. | | | |
| | Grade 4 Transaminitis (ALT/AST >20 x ULN; >20x baseline if | | | |
| | baseline is abnormal): | | | |
| | Tenalisib should be permanently discontinued. | | | |
| | Bilirubin: | | | |
| | Grade 2 (> 1.5-3 x ULN; >1.5-3 x baseline if baseline is abnormal): | | | |
| | • Maintain tenalisib dose. Monitor at least weekly until ≤ 1x | | | |
| | ULN. | | | |
| | Grade 3 (> 3 -10 x ULN; > 3 -10 x baseline if baseline is abnormal): | | | |
| | • Withhold tenalisib. Monitor at least weekly until bilirubin is ≤ | | | |
| | 1x ULN. | | | |
| | • Restart tenalisib at one dose lower*. | | | |
| | Grade 4 (> 10 x ULN; >10 x baseline if baseline is abnormal): | | | |
| | Discontinue tenalisib permanently. | | | |
| Other non-hematologic to | xicities | | | |
| Grade 1 or 2 | None | | | |
| Grade 3 | Withhold tenalisib dose until toxicity Grade ≤2. Restart tenalisib at | | | |
| | one dose lower* if warranted. | | | |
| Recurrence of grade 3 | Withhold tenalisib dose until toxicity Grade ≤2; Restart tenalisib at | | | |
| toxicity | one dose lower* or discontinue treatment. | | | |
| Grade 4 | Withhold tenalisib dose until toxicity Grade ≤2; Restart tenalisib at | | | |
| | one dose lower* or discontinue tenalisib. | | | |
| Recurrence of grade 4 | Discontinue tenalisib | | | |

toxicity

*See 'Guidelines for dose reduction' below.

Note: The drug interruption and dose modification should be discussed with medical monitor.

Page 49 of 66 CONFIDENTIAL

| Table 6. Guidance on Tenansio Dose reduction | | | | | | |
|--|--------------------|--------------------------------|--------------------------------|--|--|--|
| Group | 1st Dose reduction | 2 nd Dose reduction | 3 rd Dose reduction | | | |
| Group 1 (Tenalisib 800 mg BID) | 400 mg BID | Discontinue | - | | | |

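### Protocol Table 7 prints no action for ALT/AST of >3-5 x ULN at normal baseline, because the Grade 1-2 row stops at 3 x; the Table 6 platelet cut-offs (25 and 20) also do not meet

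*Protocol*

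**What the plan says.** Table 7 (Protocol 7.6, Hepatic) grades ALT/AST on two scales. The first row reads "Grade 1-2 Transaminitis (ALT/AST >1-3 x ULN if baseline is" and continues "normal; 1.5 -3 x baseline if baseline is abnormal". Its action is to keep the dose, start prednisone 40 mg daily and check weekly. The same row adds a conditional stop: "Withhold tenalisib in case of development of grade 2" transaminitis, or if Grade 1 worsens, while the patient is on steroids.

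The next row is "Grade 3 Transaminitis (ALT/AST >5–20 x ULN; >5-20 x" baseline if that is abnormal. Its action begins "Withhold tenalisib and monitor ALT/AST twice a weekly until" Grade 1 or lower, with restart one dose lower. Grade 4 starts above 20 x on either scale and ends treatment for good.

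Table 6 prints the Grade 3 platelet row down to 25 x10^9/L (with Grade 1 bleeding, maintain dose). It prints the Grade 4 row at 20 x10^9/L (or Grade 3 with Grade 2 bleeding, hold dose).

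Section 7.6 presents both tables as guidance under the investigator's judgement, and a note under each asks for discussion with the medical monitor. Section 4.1 admits patients with ALT/AST up to 3 x ULN, or up to "5 x ULN for patients with liver metastasis or liver involvement".

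**The concern.** A row labelled Grade 1-2 should run up to the point where Grade 3 begins. Here it stops at 3 x ULN and Grade 3 begins above 5 x ULN. At 4 x ULN, a site that goes by the label keeps the dose and starts prednisone; a site that goes by the numbers finds no hepatic instruction.

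The row concerns the toxicity this drug shows most often. Protocol 1.4 reports ALT and AST increases as the most frequent related adverse events, 15.6% each at any grade and 7.4% each at Grade 3 or above. What is at stake is consistent handling of a known liver signal across about five sites, and a clear rule for low platelets.

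**Working it through.** The plan gives no figure to reproduce. The check is whether the printed rows cover the whole range.

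**1. ALT/AST, normal baseline (Table 7)**

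| Row | x ULN | Action |
|---|---|---|
| Grade 1-2 | >1 to 3 | maintain, prednisone 40 mg daily |
| none | >3 to 5 | none printed |
| Grade 3 | >5 to 20 | withhold |
| Grade 4 | >20 | discontinue |

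Scanning upward from 1.1 in steps of 0.1, the uncovered values are 3.1 to 5.0, that is (5.0 - 3.1)/0.1 + 1 = 20 grid points.

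**2. Control: bilirubin, same table.** The ranges are >1.5-3, then "Grade 3 (> 3 -10 x ULN; > 3 -10 x baseline if baseline is abnormal", then >10. Nothing above 1.5 is uncovered, so the fault is not a feature of the table as a whole.

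**3. Who is left without an instruction.** A patient coming down from Grade 3 is covered, because that row holds drug until Grade 1 or lower. A patient already on steroids who develops Grade 2 is covered by the conditional stop. That leaves mainly a first value of >3-5 x ULN in a patient not yet on steroids.

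**4. Platelets (Table 6).** On the evident direction, Grade 3 is 25 to <50 and Grade 4 is <20 x10^9/L, so 20 to <25 has no row. Taken literally, the Grade 4 sign points the other way (above 20): the row would cover 20 to 25 but leave counts of 20 or below without a row. The two neutrophil rows share one cut-off, 0.5 x10^9/L, and on the intended direction leave nothing open. The bleeding conditions were not part of this check.

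**5. ALT/AST, abnormal baseline.** The baseline limits (up to 3 x, then >5 x) do not meet either. With baseline b in multiples of ULN, the band between them is 3b to 5b. However, the Grade 3 and 4 rows print their ULN limits without restricting them to normal baseline. If those limits apply to everyone, anything above 5 x ULN already has a row, and a gap remains only where 3b < 5, i.e. b < 5/3 = 1.67.

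| Baseline b | 3b to 5b (x ULN) | If the ULN limits apply to everyone |
|---|---|---|
| 1.5 | 4.5-7.5 | >4.5-5 open; >5-7.5 Grade 3 |
| 2 | 6-10 | all Grade 3 |
| 3 | 9-15 | all Grade 3 |
| 4 | 12-20 | all Grade 3 |
| 5 | 15-25 | >15-20 Grade 3; >20-25 Grade 4 |

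If instead the two scales are alternatives, the whole band 3b to 5b is open. The text does not settle which is meant.

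**6. Frequency.** No rate for >3-5 x ULN is given. The related-event rates cannot supply one, because under Protocol 7.4.3 "Any grade 3 or 4 laboratory abnormalities and clinically significant grade 1 or 2 laboratory value(s) should be recorded as an AE": a Grade 1 or 2 value judged not clinically significant leaves no adverse event record.

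**The case against.** The strongest reply is that the label supplies the answer. A value of 4 x ULN lies below the printed Grade 3 threshold, so it belongs to the Grade 1-2 row: maintain, prednisone, weekly checks. The tables are guidance, the medical monitor is consulted, and SAP 5.1 records that the study closed early. All of this stands and keeps the point minor. It does not correct a limit that contradicts its own label.

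Three stronger readings are tempting and should not be drawn.

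- A reader might infer that the 3 x limit decides between maintaining and withholding drug. It does not. No withhold action is tied to 3 x; the printed triggers are >5 x, or Grade 2 or a worsening Grade 1 on steroids.
- A reader might infer a printed gap at >9-15 x ULN for entry at 3 x ULN, or >15-25 x ULN for entry at 5 x ULN. That holds only if the unrestricted ULN limits in the Grade 3 and 4 rows are set aside for abnormal baselines, which is an inference.
- A reader might treat the reversed inequality signs in Table 6 as errors of the plan. Those cells were damaged when the PDF was read, so the signs are a query against the source. The platelet finding uses digits from the same cells and an assumed direction, so it is less certain than the ALT/AST finding, whose limits are in clean text.

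**Conclusion.** The point holds, as a minor correction to safety instructions. At normal baseline, ALT/AST of >3-5 x ULN has no printed action, and the row's label and limit disagree; this rests on the printed text alone. For platelets, 20 to <25 x10^9/L has no row, assuming Grade 4 means below 20 and that the source PDF confirms the digits. At abnormal baseline the baseline limits do not meet, but the ULN limits may already cover the band entirely from a baseline of about 1.67 x ULN upward, so a gap there is a matter of reading. The number of patients affected cannot be derived from the documents. Sample size, efficacy analyses and confidence intervals are unaffected.

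**What to change.** 1. In Table 7, change the Grade 1-2 ALT/AST upper limit for normal baseline from 3 x to 5 x ULN, with the medical lead confirming against NCI-CTCAE v5.0. The rows then run >1-5, >5-20 and >20.
2. In Table 6, set Grade 4 platelets to <25 x10^9/L and correct the inequality directions, after checking the source PDF. Leave the bleeding conditions as they are.
3. For abnormal baseline, have the medical lead state which scale governs, and apply the stricter row until then. Do not add a normal-baseline restriction to the Grade 3 and 4 ULN limits, and do not extend maintain-dose to 5 x baseline by default. Together those two changes would keep a patient who entered at 5 x ULN on full dose up to 5 x 5 = 25 x ULN, where the ULN limit now printed for Grade 4 says to discontinue.
4. If dosing has ended, correct the tables before reuse. Then list by arm how ALT/AST values of >3-5 x ULN in normal-baseline patients were handled (maintained, withheld or reduced). The planned biochemistry listing (16.2.8.2.1) carries result and ULN, and the exposure listing (16.2.5.1) carries the action taken and its reason.

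The cost is two changed limits, a check of signs, one ruling by the medical lead and one cross-listing. No new data or procedures are needed. The stricter interim rule has its own price: a patient who entered at 5 x ULN would be withheld at any rise above that, for example at 5.5 x ULN, which is only 5.5/5 = 1.1 x baseline. The ruling should therefore come promptly.
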